- l. In the judgment of the Investigator, the participant has an abnormal finding on the baseline 12-lead ECG considered clinically significant.
- m. In the judgment of the Investigator, the participant has a significantly abnormal finding during the 28-day baseline period, including hematology, blood chemistry,

coagulation tests, or urinalysis values/findings (abnormal tests may be repeated for confirmation).

- n. The participant has hepatic enzymes (alanine aminotransferase [ALT], aspartate aminotransferase [AST], alkaline phosphatase [ALP]) more than  $1.5 \times$  the upper limit of normal (ULN) during the 28-day baseline period, after confirmation in a repeat test, or suspected hepatocellular damage that fulfills the criteria for Hy's law.
- o. The participant has serum creatinine more than  $1.5 \times$  the ULN, clinically significant proteinuria (urine dipstick +4), an estimated glomerular filtration rate (eGFR) of  $<75$  mL/min/1.73m^2, as calculated by the revised Schwartz formula (eGFR=[0.413×Ht]/serum creatinine), or evidence of renal disease during the 28-day baseline period.
- p. The participant has any history of alcohol or drug abuse. The definition of alcohol or drug abuse, including marijuana, is based on the Investigator's clinical judgement.
- q. In the judgment of the Investigator, the participant cannot fully participate in or successfully complete the trial for its full duration for any of the following reasons:
  - The participant is mentally or legally incapacitated, or unable to give assent/consent for any reason.
  - The participant is in custody due to an administrative or a legal decision or is in residential treatment.
  - The participant /caregiver is unable to be contacted in case of emergency.
  - The participant has any other condition, which, in the opinion of the Investigator, makes the patient inappropriate for inclusion in the trial.
  - The participant is a relative of a trial center or Sponsor employee who is directly involved in the trial.
- r. Vulnerable participants (eg, people kept in detention) whose vulnerability is based on a condition other than the age required for trial eligibility.
- s. The participant received a live attenuated vaccine (eg, intranasal flu vaccine, and measles, mumps, and rubella vaccine) within the 12-week period prior to screening.

**Note:** If a medical need arises during the trial, the participant may receive a live attenuated vaccine.

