4. GENERAL ISSUES FOR DATA ANALYSIS

4.1. General

Descriptive statistics for continuous variables include n, mean, standard deviation (SD), standard error (SE), median, minimum, and maximum. Descriptive statistics for categorical variables including participant counts, percentages and missing category will be displayed as appropriate.

Summaries of potentially clinically significant abnormal values will include all postbaseline values (including scheduled, unscheduled, and early termination visits).

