8.6. Clinical Laboratory Tests

Clinical laboratory tests (serum chemistry, hematology, coagulation, and urinalysis) will be performed using the central laboratory at the time points detailed in the trial protocol. Specific laboratory tests to be performed are listed below in [Table 3](#).

Table 3: Clinical Laboratory Tests

Serum chemistry	Hematology and coagulation	Urinalysis
Calcium	Hemoglobin	Color and appearance
Phosphate	Hematocrit	Protein
Sodium	RBC count	Glucose
Potassium	RBC indices	Ketones
Chloride	mean corpuscular volume	Blood
Creatinine	mean corpuscular hemoglobin concentration	Leukocyte esterase
Glucose	RBC distribution width	Nitrite
BUN	Platelets	Bilirubin
ALT	Leukocytes	pH
AST	neutrophils	Specific gravity
LDH	lymphocytes	Microscopic tests
GGT	eosinophils	bacteria
Alkaline phosphatase	monocytes	erythrocytes
Creatine phosphokinase	basophils	leukocytes
Carbon dioxide	Prothrombin time	crystals
Magnesium	Partial thromboplastin time	casts
Protein	INR	
Albumin		
Bilirubin (total and direct)		

ALT=alanine aminotransferase; AST=aspartate aminotransferase; BUN=blood urea nitrogen; GGT=gamma-glutamyl transpeptidase; INR=International Normalized Ratio; LDH=lactate dehydrogenase; RBC=red blood cell.

Laboratory tests results and changes from baseline for chemistry, hematology, urinalysis, and coagulation laboratory tests will be summarized by visits for each treatment group using descriptive statistics. Shifts (below, within, and above the normal range) from baseline to each visit and Last Assessment will be summarized using participant counts. Listings of all individual participants' laboratory test results will be presented.

All clinical laboratory test results outside of the reference range will be judged by the Investigator as belonging to one of the following categories:

- abnormal and not clinically significant
- abnormal and clinically significant

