A laboratory test result that is judged by the Investigator as clinically significant will be recorded both on the source documentation and the CRF as an adverse event. The incidence of potentially clinically significant abnormal results will be summarized using descriptive statistics with the criteria specified in [Table 4](#). The potentially clinically significant abnormal laboratory values will include all postbaseline values (including scheduled, unscheduled, and early termination visits) for the summaries. Listings of participants who have potentially clinically significant abnormal laboratory data will be presented.

Table 4: Criteria for Potentially Clinically Significant Laboratory Values

Test	Pediatric 6-11 Years Criterion Value	Pediatric 12-17 Years Criterion Value
Serum chemistry		
ALT	$\geq 2x$ ULN	$\geq 2x$ ULN
AST	$\geq 2x$ ULN	$\geq 2x$ ULN
ALP	$\geq 3x$ ULN	$\geq 3x$ ULN
GGT	$\geq 3x$ ULN	$\geq 3x$ ULN
LDH	$\geq 2x$ ULN	$\geq 2x$ ULN
BUN	≥ 9.0 mmol/L	≥ 9.0 mmol/L
Creatinine	≥ 100 μ mol/L	≥ 150 μ mol/L
Bilirubin (total)	≥ 34.2 μ mol/L	≥ 34.2 μ mol/L
Hematology		
Hematocrit	Males < 0.30 L/L Females < 0.30 L/L	< 0.32 L/L < 0.31 L/L
Hemoglobin	Males ≤ 100 g/L Females ≤ 100 g/L	≤ 110 g/L ≤ 100 g/L
WBC counts	$\leq 3 \times 10^9$ /L $\geq 20 \times 10^9$ /L	$\leq 3 \times 10^9$ /L $\geq 20 \times 10^9$ /L
Eosinophils	$\geq 10\%$	$\geq 10\%$
ANC	$\leq 1 \times 10^9$ /L	$\leq 1 \times 10^9$ /L
Platelet counts	$\leq 75 \times 10^9$ /L $\geq 700 \times 10^9$ /L	$\leq 75 \times 10^9$ /L $\geq 700 \times 10^9$ /L
Urinalysis		
HGB	≥ 2 unit increase from baseline	≥ 2 unit increase from baseline
Glucose	≥ 2 unit increase from baseline	≥ 2 unit increase from baseline
Ketones	≥ 2 unit increase from baseline	≥ 2 unit increase from baseline
Total protein	≥ 2 unit increase from baseline	≥ 2 unit increase from baseline
Coagulation		
INR	>1.5	>1.5

ALP=alkaline phosphatase; ALT=alanine aminotransferase; ANC=absolute neutrophil count AST=aspartate aminotransferase; BUN=blood urea nitrogen; GGT=gamma- glutamyl transpeptidase; HGB=hemoglobin; INR=international normalized ratio; LDH=lactate dehydrogenase; RBC=red blood cell; ULN=upper limit of normal range; WBC=white blood cell

Serum β -HCG tests will be performed for all female participants who are postmenarchal or ≥ 12 years of age at screening (visit 1) and visit 5; urine β -HCG tests will be performed at all other visits. Any participant who becomes pregnant during the trial will be withdrawn.

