8.8. Vital Signs

Vital signs (pulse, systolic and diastolic blood pressure, temperature, and respiratory rate) will be measured at any time during the visit, but method for measuring temperature in an individual participant must be the same at each time point.

For any abnormal vital sign finding, the measurement should be repeated as soon as possible. Any vital sign value that is judged by the Investigator as a clinically significant change (worsening) from a baseline value will be considered an adverse event.

Vital signs values and changes from baseline to each visit and Last Assessment will be summarized using descriptive statistics. The incidence of potentially clinically significant abnormal values will be summarized for selected vital signs using descriptive statistics.

Table 5 specifies the criteria for identifying vital signs as potentially clinically significant abnormal. Note that in order to be identified as potentially clinically significant abnormal, a value would need to meet both conditions below: ie, have a value beyond the criterion value and a change of at least the magnitude specified in the change from baseline column. The potentially clinically significant abnormal vital signs values will include all postbaseline values (including scheduled, unscheduled, and early termination visits) for the summaries.

Table 5: Criteria for Potentially Clinically Significant Vital Signs

Vital Sign	Pediatric 6-11 Years Criterion Value	Pediatric 12-17 Years Criterion Value	Change relative to baseline
Pulse	≥ 140 bpm	≥ 120 bpm	Increase of ≥ 15
	≤ 60 bpm	≤ 50 bpm	Decrease of ≥ 15
Systolic blood pressure	≥ 135 mm Hg	≥ 150 mm Hg	Increase of ≥ 20
	≤ 80 mm Hg	≤ 85 mm Hg	Decrease of ≥ 20
Diastolic blood pressure	≥ 93 mm Hg	≥ 100 mm Hg	Increase of ≥ 15

Vital Sign	Pediatric 6-11 Years Criterion Value	Pediatric 12-17 Years Criterion Value	Change relative to baseline
	≤ 37 mm Hg	≤ 44 mm Hg	Decrease of ≥ 15
Respiratory rate	<15 breaths/min	<10 breaths/min	
Body temperature	$\geq 38.3^{\circ}\text{C}$	$\geq 38.3^{\circ}\text{C}$	Change of $\geq 1.1^{\circ}\text{C}$

bpm=beats per minute

A listing for potentially clinically significant abnormal vital signs will be presented.

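### For 15 of the 19 laboratory tests in SAP Table 4, the counts of potentially clinically significant values do not separate new findings from values already beyond the limit at baseline

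*SAP*

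**What the plan says.** SAP 4.1 sets the general rule: "Summaries of potentially clinically significant abnormal values will include all postbaseline values". SAP 8.6 repeats it for laboratory data ("The potentially clinically significant abnormal laboratory values will include all postbaseline values (including scheduled, unscheduled, and early termination visits) for the summaries") and states the output: "The incidence of potentially clinically significant abnormal results will be summarized using descriptive statistics with the criteria specified in" Table 4. Neither section asks whether the participant already met the limit before treatment.

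Elsewhere the SAP does refer to baseline:

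- The four urinalysis rows of Table 4 are defined as at least a "2 unit increase from baseline".
- For vital signs (SAP 8.8), a flagged value must "have a value beyond the criterion value and a change of at least the magnitude specified in the change from baseline column". Respiratory rate is the one row of Table 5 with no change entry.
- SAP 8.6 plans summaries of change from baseline by visit, listings of all individual results, and shift tables: "Shifts (below, within, and above the normal range) from baseline to each visit and Last Assessment will be summarized using participant counts".

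At entry, Protocol 5.4 sets numeric limits for ALT, AST and ALP (exclusion n) and for creatinine and eGFR (exclusion o). Other laboratory findings rest on Investigator judgment. Exclusion m applies when, in that judgment, "the participant has a significantly abnormal finding during the 28-day baseline period, including hematology, blood chemistry" or coagulation or urinalysis. Exclusion c covers clinically significant disease at the Investigator's discretion, and inclusion j (Protocol 5.3) requires good health.

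SAP 8.1 presents safety data as 225 mg, 120 mg and one placebo column, plus a total.

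**The concern.** A PCS table is usually read as a list of what went wrong on treatment. With absolute limits and no baseline condition, a child with eosinophils of 12% at screening and 11% at visit 3 is counted (the limit is 10%), although nothing has worsened. No planned table separates that child from one who crossed the limit after dosing.

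The shift tables do not fill the gap, because they use the normal range and not the Table 4 limits. A child above normal at baseline who later passes a PCS limit, and a child beyond the PCS limit both times, both appear as above-to-above.

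At stake is how clearly a descriptive safety table can be read. The layout adds to the problem. Dose is set by weight, so each active column holds one weight class while placebo pools both. Carried-in abnormalities that vary with weight or age would then differ between columns with no drug effect. No efficacy analysis is involved.

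**Working it through.** The plan states no figure that this point depends on, so there is none to reproduce. The check has four steps.

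**1. Count the criteria in SAP Table 4.**

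| Group | Tests | Baseline condition |
|---|---|---|
| Chemistry | 8 | none |
| Hematology | 6 | none |
| Coagulation (INR) | 1 | none |
| Urinalysis | 4 | increase from baseline |

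The total is 8 + 6 + 1 + 4 = 19, of which 19 − 4 = 15 (79%) have no baseline condition.

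**2. Compare with the numeric entry limits.**

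- ALT, AST and ALP above 1.5× ULN, confirmed on repeat, are excluded. Table 4 flags them at 2×, 2× and 3× ULN, so entry while already flagged is largely blocked.
- Creatinine is also blocked in practice. With the protocol's formula, eGFR = 0.413 × height / creatinine (assuming cm and mg/dL), an eGFR of at least 75 needs a height of about 205 cm at 100 µmol/L and about 308 cm at 150 µmol/L, the two Table 4 limits.
- That leaves 15 − 4 = 11 tests with no numeric entry limit: GGT, LDH, BUN, bilirubin, hematocrit, hemoglobin, WBC, eosinophils, ANC, platelets and INR.
- One conflict affects ALT and AST. Protocol 12.2.1 describes participants with baseline values of 2× to 3× ULN as enrollable, which contradicts exclusion n.

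**3. Effect on a two-arm comparison (illustration).** The documents give no baseline PCS rate, so every input here is an assumption: p0 is the share beyond a limit at baseline, 80% of those are still beyond it later, and new onset is 3% versus 1%.

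Apparent rate = 0.8 × p0 + (1 − p0) × new-onset rate.

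| p0 | Active | Placebo | Ratio | Difference (points) |
|---|---|---|---|---|
| 0% | 3.00% | 1.00% | 3.00 | 2.00 |
| 2% | 4.54% | 2.58% | 1.76 | 1.96 |
| 5% | 6.85% | 4.95% | 1.38 | 1.90 |
| 8% | 9.16% | 7.32% | 1.25 | 1.84 |

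At p0 = 5%, for example, active is 0.04 + 0.95 × 0.03 = 6.85%. The difference shrinks only by the factor (1 − p0), so 92% to 98% of it is kept. With 139 randomized per group, 139 × 0.8 × p0 gives 5.6 carried-in children per group at 5% (2.2 at 2%, 8.9 at 8%).

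**4. Effect on the dose columns (illustration).** Assume 2% of children at or above 45 kg and 8% below 45 kg meet a limit at baseline, 80% persist, and there are no new cases.

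- 225 mg column: 0.8 × 2% = 1.6%
- 120 mg column: 0.8 × 8% = 6.4%
- Placebo, if 70% weigh at least 45 kg: 0.7 × 1.6% + 0.3 × 6.4% = 3.0%. The figure is 4.0% if 50% do, and 2.6% if 80% do.

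The columns differ although no treatment has any effect.

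**The case against.** A reader might infer that the whole PCS table presents old abnormalities as on-treatment findings and dilutes any safety signal. The documents do not support that, for four reasons.

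- Four of the 19 tests already require an increase, and four more are largely screened out at entry.
- The PCS table does not stand alone. The SAP also plans changes from baseline, shift tables and listings. Clinically significant results are recorded as adverse events, and possible liver injury is assessed separately (SAP 8.4).
- The SAP plans descriptive statistics and no arm ratio, and step 3 shows that the risk difference hardly moves.
- The SAP calls these values postbaseline, not new. It uses the word incidence for medical history and prior medication too (SAP 5.4 and 5.5), where new onset is impossible.

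These points stand, and they make the matter minor. The limits also differ widely in rarity, so one assumed range of 2% to 8% cannot describe all 11 tests.

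It is also fair to object to replacing the current count with a new-onset-only count. Scheduled laboratory draws are at visits 1, 3 and 5, and Protocol 8.3.4.1 takes screening as baseline. One transient abnormal draw would remove a child from the table for that test, and a child who starts beyond a limit and worsens would drop out too. The vital-sign rule would still count a child who worsens by enough. This is a reason to split the counts and not to restrict them.

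Finally, setting weight-defined dose columns against pooled placebo is a wider issue. New-onset rates can also vary with age or weight, so a split removes only the carried-in part.

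What remains is that no planned table shows which PCS values are new, although the data to do so are collected.

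**Conclusion.** The point holds as a cheap improvement to descriptive safety reporting. For 15 of 19 tests the counts mix new and pre-existing values, and for 11 of those only Investigator judgment limits entry of children already beyond the limit. Under the stated assumptions the between-arm ratio is clearly attenuated (3.0 to between 1.76 and 1.25), while the risk difference is nearly unchanged (2.0 to between 1.96 and 1.84 points). The practical risk is greatest when the 225 mg or 120 mg column is read against pooled placebo. The true size is unknown because no baseline PCS rate is given. The gap does not show that a signal would be missed, and it has no bearing on the efficacy results.

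Separately, exclusion n and the text in Protocol 12.2.1 on baseline ALT or AST of 2× to 3× ULN contradict each other and must be reconciled.

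**What to change.** In SAP 8.6, keep the PCS counts over all postbaseline values and keep the listings. For the 15 absolute-limit tests, add a split by baseline PCS status and treatment group:

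- limit not met at baseline, with those participants as the denominator;
- limit already met at baseline;
- baseline missing.

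A baseline-by-postbaseline PCS shift table would do this. The urinalysis rows need no change.

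The cost is a small programming task and a somewhat larger table, with no new data. Baseline status will usually rest on one screening draw, so a transient abnormality can misclassify a child. Keeping the all-values counts limits that harm. The note to file at the end of the SAP says the analysis has been conducted. If so, the table can be reported as an additional analysis in a CSR appendix, the route SAP 2.5.2 gives for analyses it does not list.

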8.7. Physical Examinations

Physical examinations, including height and weight (to be obtained at the screening visit, randomization visit, and EOT only) and puberty status (at randomization and EOT only) will be performed at the selected time points during the trial. Body mass index will be calculated at screening and randomization.

A complete physical examination will include the following organ systems: general appearance; head, eyes, ears, nose, and throat; chest and lungs; heart; abdomen; musculoskeletal; skin; lymph nodes; and neurological. Any physical examination finding that is judged by the Investigator as a potentially clinically significant change (worsening) compared with a baseline value will be considered an adverse event and recorded on the CRF.

8.8. Vital Signs

Vital signs (pulse, systolic and diastolic blood pressure, temperature, and respiratory rate) will be measured at any time during the visit, but method for measuring temperature in an individual participant must be the same at each time point.

For any abnormal vital sign finding, the measurement should be repeated as soon as possible. Any vital sign value that is judged by the Investigator as a clinically significant change (worsening) from a baseline value will be considered an adverse event.

Vital signs values and changes from baseline to each visit and Last Assessment will be summarized using descriptive statistics. The incidence of potentially clinically significant abnormal values will be summarized for selected vital signs using descriptive statistics.

Table 5 specifies the criteria for identifying vital signs as potentially clinically significant abnormal. Note that in order to be identified as potentially clinically significant abnormal, a value would need to meet both conditions below: ie, have a value beyond the criterion value and a change of at least the magnitude specified in the change from baseline column. The potentially clinically significant abnormal vital signs values will include all postbaseline values (including scheduled, unscheduled, and early termination visits) for the summaries.

Table 5: Criteria for Potentially Clinically Significant Vital Signs

Vital Sign	Pediatric 6-11 Years Criterion Value	Pediatric 12-17 Years Criterion Value	Change relative to baseline
Pulse	≥ 140 bpm	≥ 120 bpm	Increase of ≥ 15
	≤ 60 bpm	≤ 50 bpm	Decrease of ≥ 15
Systolic blood pressure	≥ 135 mm Hg	≥ 150 mm Hg	Increase of ≥ 20
	≤ 80 mm Hg	≤ 85 mm Hg	Decrease of ≥ 20
Diastolic blood pressure	≥ 93 mm Hg	≥ 100 mm Hg	Increase of ≥ 15

Vital Sign	Pediatric 6-11 Years Criterion Value	Pediatric 12-17 Years Criterion Value	Change relative to baseline
	≤ 37 mm Hg	≤ 44 mm Hg	Decrease of ≥ 15
Respiratory rate	<15 breaths/min	<10 breaths/min	
Body temperature	$\geq 38.3^{\circ}\text{C}$	$\geq 38.3^{\circ}\text{C}$	Change of $\geq 1.1^{\circ}\text{C}$

bpm=beats per minute

A listing for potentially clinically significant abnormal vital signs will be presented.

8.9. Electrocardiography

ECGs will be performed in triplicate, with approximately 1 minute between recordings. The average of the recorded measurements will be calculated for each visit.

Any ECG finding that is judged by the Investigator as a potentially clinically significant change (worsening) compared with the baseline value will be considered an adverse event.

For ECG variables, the mean of recorded results from last three measurements at a visit will be calculated. The mean results and mean changes from baseline to each visit in the treatment period and Last Assessment (see Section 4.4) will be summarized using descriptive statistics. Baseline is determined based on the last set of observed data before the administration of the 1st dose of the IMP.

For ECG findings, the worst value of recorded from last three findings at a visit will be used for analysis. Baseline ECG findings and shifts (normal, abnormal not clinically significant, and abnormal clinically significant) from baseline to each visit in the treatment period, Overall (worst value for a participant), and the Last Assessment (worst value of recorded findings from the last visit) will be summarized using participant counts.

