### **8.3.3.      *Electrocardiograms***

Twelve-lead ECGs will be conducted at any time during the visit, prior to IMP administration, as detailed in [Table 1](#). The ECGs should be performed after the participant has been supine for at least 5 minutes. The ECGs will be performed in triplicate, with at least 1 minute between recordings.

A qualified physician at a central diagnostic center will be responsible for interpreting the ECG. ECGs should be performed and transmitted according to the central ECG reading instructions provided in the ECG user manual. ECG equipment will be provided to all clinical sites.

Although the ECG interpretation will be performed centrally, the clinical evaluation remains under the Investigator's responsibility.

The ECG will be evaluated by the Investigator at the time of recording (signed and dated), and the printout should be kept in the source documentation file. When potentially clinically significant findings are detected by the Investigator, a cardiologist should be consulted for a definitive interpretation. All communications and diagnoses should be filed in the source documentation file. The Investigator's interpretation will be recorded in the CRF regardless of the central reading interpretation. Any abnormal findings assessed by the Investigator as clinically significant should be recorded in the relevant CRF modules (eg, adverse event, medical history).

Objective alerts are predefined as described in the central ECG reading manual. In these cases, the site and the Sponsor will be informed immediately.

Any unscheduled ECGs must also be submitted for central ECG reading.

Any ECG finding that is judged by the Investigator as a potentially clinically significant change (worsening) compared with a baseline value will be considered an adverse event, recorded on the source documentation and transcribed onto the CRF, and monitored as described in Section 8.4.5.

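### SAP 8.9 takes the worst ECG finding from only the last three at a visit, so an abnormal finding can drop out of the shift table if extra tracings are recorded

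*SAP*

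**What the plan says.** Protocol 8.3.3 plans one set of three tracings per visit: "The ECGs will be performed in triplicate, with at least 1 minute between recordings". SAP 8.9 agrees on the number: "ECGs will be performed in triplicate, with approximately 1 minute between recordings". Protocol 8.3.3 also foresees extra tracings: "Any unscheduled ECGs must also be submitted for central ECG reading".

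For the categorical reading (normal, abnormal not clinically significant, abnormal clinically significant), SAP 8.9 uses this rule: "For ECG findings, the worst value of recorded from last three findings at a visit will be used for analysis". Shifts from baseline are tabulated for each visit and for two further rows. One is "Overall (worst value for a participant"), whose source data are not stated. The other is described as "the Last Assessment (worst value of recorded findings from the last visit) will be summarized using participant counts", with no limit to three.

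For the numeric ECG variables, SAP 8.9 has two averaging sentences. The first reads "The average of the recorded measurements will be calculated for each visit". A later one takes the mean of only the last three measurements.

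SAP 4.4 has a general rule for several assessments at one visit, but exempts triplicate ECGs and refers to 8.9. Section 8.9 does not mention repeat or unscheduled tracings. For laboratory tests and vital signs there is a separate safeguard in SAP 4.1: "Summaries of potentially clinically significant abnormal values will include all postbaseline values", including unscheduled and early termination visits. Sections 8.6 and 8.8 apply it using the criteria in Tables 4 and 5. The SAP has no corresponding criteria table for ECG.

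**The concern.** A limit to the last three findings does nothing until there are more than three. It therefore acts only on visits with extra tracings, and there it discards the earlier ones. For a rule meant to report the worst finding, that can only remove abnormal findings or leave the result unchanged.

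What is at stake is the ECG findings table for a safety endpoint listed in Protocol 3.1 and SAP 1.1. A reader of a worst-value table will assume that it contains the worst recorded value. For laboratory tests and vital signs, a value superseded at the same visit still reaches the potentially clinically significant summary. ECG has no equivalent route in the SAP, although Protocol 9.5 discusses laboratory, ECG and vital signs data together and then commits to comparing all values with predefined criteria. SAP 15 does not list the absence of ECG criteria as a change.

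**Working it through.** The plan states no figure to reproduce. The check applies two rules to example sequences of findings at one visit (N = normal, A = abnormal): the SAP rule (worst of the last three) and the alternative (worst of all findings at the visit).

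| Findings in order | SAP rule | Worst of all |
|---|---|---|
| N, A, N | A | A |
| A, N, N | A | A |
| N, A, N, N | A | A |
| A, N, N, N | **N** | **A** |
| A, A, A, N | A | A |
| A, A, A, N, N, A | A | A |
| A, A, A, N, N, N | **N** | **A** |

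The rules differ only when more than three findings are recorded under the visit and the last three are all normal. With exactly three they are identical. One normal tracing after an abnormal triplicate does not hide it.

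**Relative loss in by-visit abnormal counts.** Let r be the share of abnormal visits with further tracings under the same visit, enough to displace the abnormal ones, and q the share of those in which the last three are all normal. The relative loss is r × q. Neither value is in the documents, so these are assumptions:

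- r = 0: loss 0%.
- r = 10%, q = 50%: 0.10 × 0.50 = 5%.
- r = 50%, q = 50%: 0.50 × 0.50 = 25%.
- r = 100%, q = 100%: loss 100%, the mathematical limit only.

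**Overall row.** SAP 8.9 gives the row as the worst value for a participant, directly after the sentence that sets the last-three rule for analysis. Building Overall from those per-visit values is a natural reading. Building it from every finding is also compatible with the words.

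**Last Assessment row.** Take A, A, A, N, N, N at visit 5 for a participant whose last visit is visit 5. The visit 5 row gives N. The Last Assessment row, read as worded, gives A. The same visit then appears in two categories of one table.

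**Numeric means.** With three tracings the two averaging sentences agree. With six, one averages six values and the other averages three.

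**The case against.** The case against giving this weight is substantial, and most of it stands.

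- Under the planned design the rule loses nothing, so the title endpoint is reported in full for every visit with one triplicate.
- A reader might infer that extra tracings are taken because the first set was abnormal, so that the rule hides abnormality systematically. The documents do not say so. An instruction to repeat an abnormal measurement exists for vital signs (Protocol 8.3.2, SAP 8.8) but not for ECG; for potentially clinically significant findings Protocol 8.3.3 calls for a cardiologist to be consulted.
- A reader might infer that a clinically significant ECG abnormality could vanish from the trial report. It would not. Under Protocol 8.3.3 and SAP 8.9, a change that the Investigator judges a potentially clinically significant worsening is an adverse event, and adverse events are summarised and listed whatever the shift table shows.
- A reader might infer that shifts from baseline are biased in one direction. They are not. Baseline is the last set before the first dose, so a normal repeat before dosing can replace an abnormal set and add normal-to-abnormal shifts.
- The same rule applies in both arms.
- Taking the worst of literally all tracings would bring technically invalid recordings back into the table.
- SAP 5.6 also summarises ECG findings overall and at the last visit. However, it sits under trial population and does not say which tracings count, so it is not a dependable recovery route.

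What remains is narrower. An abnormal finding judged not clinically significant is a category of the shift table in its own right. It does not become an adverse event by that route, and no all-values summary picks it up. The undefined source of the Overall row and the differently worded Last Assessment row remain whatever the repeat rate.

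**Conclusion.** The point holds as a minor one. By-visit postbaseline abnormal counts can be understated, and Overall counts too if that row is built from the per-visit values. This requires more than three tracings under a visit with the last three all normal. For these counts the error can only go downward; for shifts from baseline it can go either way.

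The amount is unknown. It is probably small, because one triplicate per visit is planned and no ECG section instructs a repeat. If no visit has more than three tracings, the effect is exactly zero. The exposure lies mainly in the category abnormal but not clinically significant. Efficacy, power and type I error are not affected.

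A firm statement that abnormal ECGs are understated in this trial would go beyond the documents. They support only that the rule permits it, and that SAP 8.9 leaves the inputs of its summary rows unclear or inconsistent.

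**What to change.** In SAP 8.9:

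1. Derive the by-visit, Overall and Last Assessment findings from all evaluable postbaseline ECG findings, including repeat and unscheduled ones. Leave out only tracings documented as technically invalid.
2. Say explicitly what the Overall row draws on, and word the Last Assessment row to match.
3. Keep the last-three rule for the numeric interval means only, and reword the two averaging sentences so that they name the same set of measurements.

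The note to file appended to the SAP indicates that the analysis has been run. The practical step is therefore to count visits with more than three ECG findings. If there are none, one sentence in the clinical study report closes the point. If there are some, rerun the findings table under the revised rule and report the change there.

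The cost is a few lines of SAP text and one derivation change. The downside is that slightly more abnormal findings may be displayed, and that technically invalid tracings have to be identified from documentation.
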